8.4.13 Side Effects

See the Comprehensive Adverse Events and Potential Risks List (CAEPR) in Section [5.3.3](#) for list of side effects.

8.4.14 Nursing/Patient Care Implications

Trametinib should be taken on an empty stomach, at least 1 hour before or 2 hours after a meal/snack. Do not take a missed dose within 12 hours of the next dose.

Advise women study participants of reproductive potential to use effective contraception while receiving study treatment and for 4 months after the last dose of trametinib. Advise women not to breastfeed while receiving study treatment and for 4 months after the last dose of trametinib. Advise men study participants to use barrier contraception and not to father a child while taking study treatment and for 4 months after the last dose of trametinib.

Rev. Add20

9. Statistical Considerations

9.1 Study Design and Objectives

In this randomized phase III study, patients with unresectable stage III or stage IV BRAFV600 mutant melanoma will be equally randomized to A: ipilimumab-nivolumab (with subsequent dabrafenib in combination with trametinib) or B: dabrafenib in combination with trametinib (with subsequent ipilimumab-nivolumab) using the stratification factors (ECOG PS, Serum LDH). The stratified randomization will be based on the permuted block method.

The primary objective is to evaluate whether initial treatment with either combination ipilimumab-nivolumab (with subsequent dabrafenib in combination with trametinib) or dabrafenib in combination with trametinib (with subsequent ipilimumab-nivolumab) significantly improves 2 year overall survival.

9.2 Study Endpoints

Overall Survival (OS) is defined as the time from randomization to death from any cause. Patients who have not died will be censored at the date of last known alive. 2-year OS rate will be defines as a proportion of patients who are alive after two years of follow-up time among all cases who have died within 2 years or alive after 2-year follow-up time.

Progression-Free Survival (PFS) is defined as the time from randomization to disease progression or death (whichever occurs first). Cases without an event to date will be censored at the date of last disease assessment documenting the patient was free of progression. Progression will be evaluated based on international criteria proposed by the revised Response Evaluation Criteria in Solid Tumors (RECIST) guideline (version 1.1) as described in Section [6.1](#).

Response will be defined by the RECIST guidelines (version 1.1) as described in Section [6](#).

Toxicity will be defined using the CTCAE version 4.0 criteria.

9.3 Sample Size Considerations and Monitoring Plan

The primary comparison will be overall survival (OS) in arms A: ipilimumab-nivolumab (with subsequent dabrafenib in combination with trametinib) vs. B: dabrafenib in combination with trametinib (with subsequent ipilimumab-nivolumab). The primary endpoint for this study is the 2-year overall survival (OS) rate. Since the proportional hazard assumption is not appropriate for the proposed treatment arms, the most meaningful endpoint is the 2-year OS rate. The sample size calculation was conducted using the 2-year OS as a binary data. The primary analysis will be an ITT analysis based on the 2-year OS rate, using the Mantel-Haenszel test. The number of cases censored before two years is expected to be minimal in this study.

The sample size for 2-year OS rate of 70 % in arm A vs. 50% in arm will be 270 for 90% power. This is based on the two-sided type I error rate of 0.05 and allows for three interim analyses. An additional 10% (30 patients) have been added to cover for potential ineligibility or patient loss at the crossover time point. Assuming accrual rate of 16 (based on E2603/E1608 40/month and a 40%

BRAFV600 mutation rate seen in E2603) accrual is estimated to take a maximum of 19 months. In addition, the follow-up time will be 2 years to assess the 2-year OS rate endpoint. Note that a clinically meaningful difference in 2-year OS rate is 70% vs. 50%. This assumption was used for the above power calculation of 90%. However if there is slightly smaller difference, i.e. 67.5% vs. 50%, the proposed design still provides 80% power.

Formal interim analysis based on the difference of 2-year OS rate between the two arms will be conducted, starting at 33% information time (that is when first 100 patients enrolled are followed for 2 years). We expect this will be around 30 months (2.52 years) after the study activates. After that, interim analysis will be repeated every 6 months. It is expected to be at 65% and 100% information time. To preserve the overall type I error rate, critical values at the interim analyses will be determined using a truncated version of the Lan-DeMets spending function corresponding to the O'Brien-Fleming boundary. Table 1 below summarizes operating characteristics of the proposed monitoring plan.

This study will also be monitored for early stopping in favor of the null hypothesis based on the Jennison-Turnbull repeated confidence interval (RCI) approach. At each interim analysis, the difference in 2-year OS rates in arms A and B and variance will be estimated. The RCI on the difference in 2-year OS rates will be computed using the critical value from the error spending rate function and estimated variance. Strata will be taken into account for the RCI monitoring. If this RCI does not include the target alternative difference, then the study may be stopped early for lack of benefit.

Table 1. Operating Characteristics of Interim Analyses

Repeated Analyses	Real Time (years)	Total No. Of cases 2-yr OS assessed	Information Time	Upper Boundary	Nominal Significance
1	2.52	100	.33	3.7307	0.954874E-04
2	3.02	196	.65	2.5498	0.538891E-02
3	3.56	300	1	1.9903	0.232812E-01

Starting from 1 year after activation and every 6 months subsequently, the following issues will also be discussed at the ECOG-ACRIN DSMC meeting. It is assumed that the hazard rates for OS will vary over the course of study. For the safety of patients, hazard ratios (HR) for OS will be monitored during the course of the study. Hazard functions for OS and HR for OS will be estimated. As an approximate guideline, the HR for OS < 0.75 or > 1.33 will prompt a discussion of the ECOG-ACRIN DSMC. The main purpose of monitoring is for the safety reason in earlier part of the study. When the formal interim analysis begins based on the 2-year OS rate (after 2.52 years), it is not likely this safety-based monitoring will indicate a conflicting result. However this issue will be reported and discussed at the ECOG-ACRIN DSMC. The ECOG-ACRIN DSMC will also monitor the feasibility of cross-over from one arm to the other and completing at least an initial course of treatment after cross-over. If less than 50% of patients

can safely cross over from one therapy to this other, accrual will be halted and the feasibility of the alternative treatment schedules will be evaluated.

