1.1 Research Hypothesis

We hypothesize that initial treatment of patients with BRAFV600 mutant melanoma with ipilimumab + nivolumab (+/- followed by dabrafenib + trametinib) will maximize their chance for therapeutic benefit and result in greater 2 year survival and more durable complete responders than initial treatment with dabrafenib + trametinib (+/- followed by ipilimumab + nivolumab).

It is conceivable, however, that this assumption is false and that either the two treatment approaches produce roughly equivalent outcome or that initial therapy with dabrafenib + trametinib results in superior 2-year survival outcome. Therefore, the study is designed with a two-tailed p value.

The results of this study will establish a data driven approach to this treatment decision for patients with BRAFV600 mutant melanoma that maximizes their chance for long-term benefit. Further, information on the relative value of initial treatment with immunotherapy vs molecularly targeted therapy may have implications for treatment choices with other immunotherapies and targeted therapies in melanoma and for other cancer types where both immunotherapy and targeted therapies have shown efficacy (e.g. RCC, NSCLC etc). Measuring the severity, duration, and overall impact of CTCAE compiled and patient-reported toxicities, symptoms and function for each treatment sequence will provide additional guidance for treatment decision-making and complement the primary endpoint of overall survival.

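### The futility rule names one unsigned target; read as +20 points for Arm A, it lets data favouring Arm B qualify for a stop in favour of the null before Arm B can be declared superior

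*Combined protocol and SAP*

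**What the plan says.** Section 1.1 allows that starting with dabrafenib + trametinib could give the better 2-year survival, and concludes: "Therefore, the study is designed with a two-tailed p value". Section 2.1 asks whether either sequence improves 2-year survival.

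Section 9.3 sizes the trial on one alternative: "The sample size for 2-year OS rate of 70 % in arm A vs. 50% in arm will be 270 for 90% power". The second rate belongs to Arm B, although its letter is missing. On error control: "This is based on the two-sided type I error rate of 0.05 and allows for three interim analyses". Section 9.1 gives equal allocation: patients "will be equally randomized to A: ipilimumab-nivolumab" or to Arm B.

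Section 9.3 then adds a futility rule, introduced as "This study will also be monitored for early stopping in favor of the null hypothesis". At each interim look an RCI for the A–B difference is built from that look's critical value and the estimated variance. The action is: "If this RCI does not include the target alternative difference, then the study may be stopped early for lack of benefit".

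No second target of −20 points is given, nothing is said about an RCI lying on Arm B's side, and Table 1 lists only an upper boundary. A separate guideline in the same section brings a survival hazard ratio below 0.75 or above 1.33 to the DSMC for discussion.

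**The concern.** A futility rule with one target suits a trial that cares about one direction. Section 1.1 says this trial cares about both. If the target is +20 points, an interim result that clearly favours Arm B excludes it, and the plan then describes a stop as being in favour of the null. What the data would be ruling out is an Arm A advantage; an Arm B advantage could still be well supported.

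At stake is the ability to conclude that Arm B first is better, which is half of the primary question. The mirror-image result favouring Arm A would simply continue, so the two sequences would not be monitored on equal terms.

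**Working it through.** **Inputs.** Sections 9.1 and 9.3: 1:1 allocation; two-sided alpha 0.05; target 70% (A) vs 50% (B). Table 1: looks at 100, 196 and 300 patients, taken as 50, 98 and 150 per arm; critical values 3.7307, 2.5498 and 1.9903.

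**The plan's own figures.**
- Uncorrected size per arm: [1.96·√(2·0.6·0.4) + 1.2816·√(0.7·0.3 + 0.5·0.5)]² / 0.20² = (1.358 + 0.869)² / 0.04 ≈ 124. With continuity correction: (124/4)·[1 + √(1 + 4/(124·0.20))]² ≈ 134, or 268 in total. This agrees with 270.
- One-sided tail areas of the three critical values are 9.55e-5, 0.00539 and 0.0233, as in Table 1. Their cumulative one-sided alpha is 0.025, so the boundaries belong to a two-sided 0.05 test although only the upper one is printed.

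**Where the rule bites.** RCI = d ± c·SE, with d = A − B and SE = √(pA·qA/n + pB·qB/n). The +20 target is excluded when d + c·SE < 0.20.
- Look 1, observed 50% vs 70%: SE = √(0.25/50 + 0.21/50) = 0.0959; half-width 3.7307 × 0.0959 = 0.358; RCI −0.558 to +0.158. It excludes +0.20, so the criterion is met, yet it contains both 0 and −0.20. The mirror result, 70% vs 50%, gives −0.158 to +0.558 and the trial continues.
- Look 2: SE = √(0.46/98) = 0.0685; half-width 2.5498 × 0.0685 = 0.175.

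| Look | Futility criterion met if d is below | Arm B declared superior if d is below |
|---|---|---|
| 1 | about −0.16 | about −0.37 |
| 2 | about +0.02 | about −0.18 |

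At both looks the futility threshold lies well above Arm B's efficacy boundary. Hand check at look 1 with true rates 50%/70%: P(d < −0.158) = Φ((−0.158 + 0.20)/0.0959) = Φ(0.44) ≈ 0.67. About 0.04 to 0.05 of this has already crossed Arm B's boundary, which leaves roughly 0.62.

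**Simulation.** Efficacy is checked first (pooled Z), then futility at looks 1 and 2 (unpooled SE). The power column headed with the rule assumes that every met criterion leads to a stop.

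| True A / B | Criterion met, look 1 + look 2 | Power for B, rule ignored | Power for B, rule always followed | Power for B, both ±20 must be excluded |
|---|---|---|---|---|
| 50 / 70 | 62% + 24% = 86% | 94.5% | 14% | 94.5% |
| 50 / 65 | 43% + 48% ≈ 90% | 74% | 9% | 74% |
| 50 / 60 | 25% + 67% ≈ 91% | 40% | 4% | 40% |

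For 50/70 with 270 or 300 patients and pooled or unpooled Z, the criterion is met in 82–86% of trials and power for B under the rule is 14–18%.

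In the other direction (70/50) the criterion is met in about 0.5%, and power for A stays near 94.5%. Under 60/60 the criterion is met in about 62%. The chance of wrongly declaring B falls from about 2.5% to 0.2%, while that for A stays near 2.5%.

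**The case against.** **The target has no sign.** The sentence defining what matters names no arm: "Note that a clinically meaningful difference in 2-year OS rate is 70% vs. 50" (per cent). In a two-sided trial, a 20-point difference in either direction is a possible reading. Under it the problem disappears: at 50/70 the criterion is met in about 0.5% of trials. This stands as a reason to ask for clarification. It does not settle the matter, because the rule refers to a single target and the only alternative tied to arms is +20.

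**The rule is permissive.** The study may be stopped; it need not be. A reader might infer that 86% of such trials would stop, or that the test is in effect one-sided. The documents support neither. The efficacy test remains two-sided, and Arm B keeps its full power if the DSMC continues.

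**The DSMC has other information.** The hazard-ratio guideline works in both directions. If survival were exponential (an illustration only, since Section 9.3 rejects proportional hazards), 50% vs 70% at 2 years is an A:B hazard ratio of ln 0.5 / ln 0.7 ≈ 1.94, and 50% vs 65% is about 1.61. Both exceed 1.33, so an Arm B advantage would probably already be under discussion. That tempers the practical risk, but the guideline prompts discussion only and does not amend the futility rule.

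**A stop does not end all inference.** Section 5.11 continues survival follow-up to 5 years, and Section 9.4 analyses all randomized patients. The loss of power describes the formal sequential decision.

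**Conclusion.** The concern holds in a limited form. Section 9.3 leaves the sign of the futility target unwritten. On the likelier reading, +20 points for Arm A, a true Arm B advantage of 10 to 20 points meets the criterion for a null stop about 86–91% of the time, before Arm B's boundary is reached. Power for Arm B would fall from about 94.5% to 14–18% at 50/70, and from about 74% to 9% at 50/65, if the DSMC acted each time.

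These are probabilities of meeting a criterion. They assume equal arms, no loss before 2 years, an unstratified RCI (the plan says strata will be taken into account) and efficacy assessed before futility. A reader might also infer that the asymmetry inflates type I error. It does not: it lowers the chance of declaring Arm B under no difference and leaves that for Arm A unchanged.

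**What to change.** In Section 9.3, state that:
- a stop in favour of the null requires the RCI to exclude both +20 and −20 points, so that it lies wholly between them;
- an RCI that excludes only +20 is not grounds for a null stop;
- the Table 1 boundaries apply symmetrically, with the lower boundary added to the table.

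Power for Arm B returns to about 94.5% at 50/70 and 74% at 50/65; power for Arm A is unchanged.

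**Cost.** Essentially no futility stop remains at look 1, because the half-width there is 0.34–0.37 for survival rates of 50–70%, which cannot fit inside ±0.20. At look 2, with rates near 60%, the observed difference must be within about 2 points of zero. Early null stops under no difference fall from about 62% to 25% at 60/60; under the new rule they are about 17% at 50/50 and 39% at 70/70. The lighter alternative, switching futility off whenever the estimate favours Arm B, permits fewer still (about 15% at 60/60).

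On the planned timeline the price is follow-up time and not enrolment: accrual ends by month 19 and the first look comes at about month 30. Appendix XVI shows accrual still incomplete in its July 2020 assessment, so in practice some enrolment could have been affected.

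If the interim looks have already taken place, record which reading of the target the DSMC applied.

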9.4 Statistical Analysis Plan

The primary (2-year OS rate) and secondary efficacy (OS, 3-year OS rate) analyses will include all randomized patients (intent-to-treat analysis). Toxicity analysis will be based on all cases who received the treatment regardless of eligibility.

The primary endpoint, 2-year OS rate will be estimated (proportion of patients alive after 2 years of follow-up time) and will be compared between the two arms using the Mantel-Haenszel test (stratified by ECOG PS and LDH) based on two-sided overall type I error rate of 0.05 adjusting for two-interim analysis. Mantel-Haenszel test will compare the 2-year OS rates while controlling for the stratification factors. The difference in 2-year OS rates in arms A and B will be estimated and presented with 95% repeated confidence interval of Jennison-Turnbull. In addition, OS distribution will be estimated using the Kaplan-Meier method. The distribution of OS will be compared using the stratified log rank test. Hazard of OS will be estimated as a function of time in arm A and in arm B (as randomized in step 1 to arm A vs. B) and presented graphically.

In PFS distribution will be estimated using the Kaplan-Meier method.

PFS distributions will be compared using the log rank test and response rates will be compared using the Mantel-Haenszel test (stratified by ECOG PS and LDH) test in arms A vs. B. 3-year OS rate (proportion of patients alive after 3 years of follow-up) will be estimated by treatment arms and will be compared using the Mantel-Haenszel test (stratified by ECOG PS and LDH) in arms A vs. B. Cases censored before 3-year will not be included in this analysis, but this number is expected to be minimal.

Response rate and PFS for patients who are treated with Ipilimumab/Nivolumab before crossover (arm A) vs. for patients who were initially treated with dabrafenib/trametinib and crossed over to Ipilimumab/Nivolumab will be compared (arm D). For the latter group, PFS will be defined as the time from cross-over until progression or deaths without progression. Tumor response will be assessed from the start of a particular therapy and baseline will be recalculated at time of cross over therapy. Patients without RECIST defined measurable disease at time of crossover will be excluded from the response assessment. Response rates will be compared using the Fisher's exact test and PFS will be compared using the log-rank test. Safety profile of these two groups will also be compared using the Chi-square or Fisher's exact test. Analyses specified in this paragraph will be repeated for arms B vs. C comparison.

Toxicity rate for individual AEs, categorized AEs and worst degree AEs will be compared in arms A vs. B and in arms C vs. D using the Chi-square or Fisher's exact test. Two-sided p-values will be reported for these comparisons.

In the event of missing data, it will be assumed that the data will be missing at random and no imputation will be performed.

Subset analyses are planned for all stratification factors (ECOG PS, LDH) and well known prognostic factors such as age, sex, ulceration, etc. Subset analyses are considered to be exploratory in nature.

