Several mechanisms of resistance to BRAF inhibitors have been described, and they are generally divided into MEK dependent and MEK independent resistance. Therefore, clinical trials have been conducted with a combination of BRAF and MEK inhibitors in patients with metastatic melanoma who were naïve to BRAF inhibitors as well as in patients who progressed after a BRAF inhibitor. The combination of dabrafenib 150 mg twice daily and trametinib 2 mg once daily in BRAF inhibitor-naïve patients showed responses in 41 of 54 (76%) patients compared with 29 of 54 (54%) given dabrafenib monotherapy, and longer median progression-free survival compared with dabrafenib alone (9 vs 5 months).¹³ These results led to the FDA approval of combination dabrafenib + trametinib as standard therapy for patients with BRAF V600 mutant melanoma in 2014. Recent updates for patients enrolled in the full dose dabrafenib + trametinib cohort showed a median overall survival of 25 months and a 2 year survival of 75% (56%-86%) for patients with a normal LDH compared with 18% (6%-36%) for patients with an elevated LDH.²⁵ In addition, it appears that the combination treatment was well tolerated. In particular, a significant decrease in the number of

cutaneous squamous cell carcinomas (7% vs 19%) and other skin toxicity was noted relative to dabrafenib alone. A large phase 3 randomized clinical trial of dabrafenib plus trametinib versus dabrafenib plus placebo (Combi-d) confirmed the superior efficacy of dabrafenib and trametinib over dabrafenib alone). PFS for the combination was 9.3 months vs 8.8 months for dabrafenib alone [HR 0.75; 95% CI (0.57-0.99)] and overall response rate 67% for the combination vs 51% for the single agent. On preliminary analysis, overall survival was improved with the combination (HR 0.63, 95% CI 0.42-0.94) although these results were not statistically significant, as they did not cross the predefined boundary for early stopping.²³ These results further support the use of this combination in patients with BRAF mutant melanoma.

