6.1.1 Definitions

Evaluable for Objective Response

Only those patients who have measurable disease present at baseline, have received at least one cycle of therapy, and have had their disease re-evaluated will be considered evaluable for response. These patients will have their response classified according to the definitions stated below.

NOTE: Patients who exhibit objective disease progression prior to the end of cycle 1 will also be considered evaluable.

Evaluable Non-Target Disease Response

Patients who have lesions present at baseline that are evaluable but do not meet the definitions of measurable disease, have received at least one cycle of therapy, and have had their disease re-evaluated will be considered evaluable for non-target lesion assessment. The response assessment is based on the presence, absence, or unequivocal progression of the lesions.

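### Section 9.4 does not stratify the A vs B PFS test by ECOG PS and LDH, and it names no all-randomized denominator for response

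*Combined protocol and SAP*

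**What the plan says.** Section 9.1 states that patients "will be equally randomized to A" or B "using the stratification factors (ECOG PS, Serum LDH). The stratified randomization will be based on the permuted block method".

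Section 9.4 uses those factors in four A vs B efficacy comparisons. The 2-year and 3-year OS rates are compared by a Mantel-Haenszel test stratified by PS and LDH. For survival time, "The distribution of OS will be compared using the stratified log rank test". For response, "response rates will be compared using the Mantel-Haenszel test (stratified by ECOG PS and LDH) test in arms A vs. B". The fifth comparison, PFS, opens that same sentence and is worded differently: "PFS distributions will be compared using the log rank test and response rates will be compared using the Mantel-Haenszel test", with strata named only after Mantel-Haenszel and none for the log-rank test.

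The intention-to-treat sentence in Section 9.4 names the 2-year OS rate, OS and the 3-year OS rate. It names neither PFS nor response. Section 9.2 refers the definition of response to Section 6. There, Section 6.1.1 limits evaluability: "Only those patients who have measurable disease present at baseline, have received at least one cycle of therapy, and have had their disease re-evaluated" count as evaluable, and patients with objective progression before the end of cycle 1 are added. Section 9.4 also says that missing data will be taken as missing at random, without imputation. It gives no denominator for the A vs B response rate.

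**The concern.** There are two separate issues.

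**PFS.** The protocol's own background shows that LDH is strongly prognostic on dabrafenib + trametinib. Two-year survival was "75% (56%-86%) for patients with a normal LDH compared with 18% (6%-36%) for patients with an elevated LDH" (Section 1.2). Stratified randomization balances LDH between arms and so reduces the true sampling variation of the treatment contrast. An unstratified log-rank variance does not credit that reduction, and mixing strata pulls the marginal hazard ratio toward 1. Both effects cost power. The plan gives no reason for treating PFS differently from OS.

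**Response.** A cycle is 6 weeks, and re-evaluation is every 12 weeks (Section 6.1). A patient who dies or withdraws before any scan, without documented objective progression, is not evaluable under 6.1.1. With no ITT statement for response and no imputation, the natural reading is that this patient leaves the denominator. That exclusion happens after randomization. If it is more frequent in one arm, that arm's response rate is raised relative to the other.

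**Working it through.** **The plan's own figures.** No power, alpha or event target is stated for PFS or response, so there is nothing on this point to reproduce. The 270 for the primary endpoint (70% vs 50%, two-sided 0.05, 90% power) reproduces as 268 with a continuity correction, and 270/0.9 = 300. N = 300 is used below.

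**PFS inputs.**
- From the documents: N = 300, 1:1 within PS x LDH strata; 19 months' accrual and 24 months' follow-up (Section 9.3); median PFS 9.3 months (Section 1.8).
- Assumed: PFS hazard ratio 0.70, constant over time; 40% elevated LDH; 30% PS 1; prognostic hazard ratios as tabulated.
- Upper extreme for LDH: the OS figures imply ln(0.18)/ln(0.75) = 5.96 under exponential survival. This is an OS ratio from one cohort, so it is a ceiling rather than an estimate for PFS.

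The unstratified statistic is Z = (O - E)/sqrt(V) over all patients. The stratified statistic is Z = sum(O - E)/sqrt(sum V) over the four strata. Each is tested at |Z| > 1.96, with 6,000 simulated trials per row.

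| LDH HR / PS HR | Null size, unstratified | Null size, stratified | Power, unstratified | Power, stratified |
|---|---|---|---|---|
| 1.0 / 1.0 | 5.1% | 5.4% | 81% | 80% |
| 1.5 / 1.3 | 5.0% | 5.5% | 80% | 81% |
| 2.0 / 1.5 | 3.9% | 5.3% | 74% | 80% |
| 3.0 / 1.5 | 2.6% | 4.8% | 66% | 78% |
| 5.96 / 1.5 | 1.8% | 5.4% | 45% | 75% |

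Changing the assumptions to 38% elevated LDH and a PS hazard ratio of 1.4 gives, for LDH hazard ratios of 2, 3 and 4, power of 75% vs 80%, 70% vs 81% and 64% vs 81%. The differences are 5, 11 and 17 points. A further run at the same three LDH hazard ratios gave 76% vs 82%, 69% vs 80% and 63% vs 80%, with unstratified null size of 4.4%, 3.2% and 1.9%.

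**PFS under non-proportional hazards.** With a delayed effect (for example hazard ratio 1, then 0.5), the gain from stratifying was 1 to 7 points across runs. With crossing hazards (for example 1.3 for 6 months, then 0.4), the stratified test was 1 to 6 points less powerful. These shapes are also assumptions.

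**Response illustration.** Let the true response rate be 50% in both arms, with 150 per arm, and let all non-evaluable patients be non-responders. The observed rate is 0.50/(1 - non-evaluable share).
- 15% (A) vs 5% (B) non-evaluable: 0.50/0.85 = 58.8% of 127.5 and 0.50/0.95 = 52.6% of 142.5. The pooled rate is 150/270 = 55.6% and the null SE is sqrt(0.556 x 0.444 x (1/127.5 + 1/142.5)) = 0.0606. A two-sided 0.05 test rejects about 17% of the time.
- 20% vs 5%: 62.5% vs 52.6%, rejecting about 36% of the time.
- On all randomized patients, both arms show 50% in both cases.

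The non-evaluable shares are not in the documents. With equal shares there is no distortion of this kind.

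**The case against.** The strongest objection is that Section 9.3 itself rejects proportional hazards for these arms, and Section 1.9 contrasts prolonged PFS on targeted therapy with durable response in a subset on immunotherapy. A power table built on a constant hazard ratio therefore cannot promise a gain, and under crossing hazards stratifying can cost a little. This stands: the gain is conditional. What remains is the conservatism under the null, which does not depend on the shape of the treatment effect, and the unexplained difference from the OS test.

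The stratification bracket in the same sentence might be meant to cover both tests. As written it is attached to Mantel-Haenszel, and a statistician following the text would run an unstratified log-rank.

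Several stronger readings are tempting, but the documents do not support them:
- *PFS loses ITT balance.* It does not. PFS runs from randomization, deaths count as events, and no evaluability restriction is attached to it.
- *The response test is also unstratified.* It is explicitly stratified by PS and LDH. Its weakness is comparability of the arms, not power.
- *The 21% stopping ipilimumab + nivolumab for adverse events (Section 1.5) is the non-evaluable share.* Section 5.1.5 keeps imaging patients who stop for reasons other than progression, so a patient who completes cycle 1 and then stops for toxicity should still be scanned.
- *Entry criteria add to the exclusions.* Measurable disease is required for entry (Section 3.1.6), so that part of 6.1.1 should remove nobody eligible for Step 1.

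Use of the 6.1.1 set for A vs B remains an inference, because Section 9.4 names no set. That silence is what needs correcting.

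**Conclusion.** The point holds in limited form. The A vs B PFS test is the only A vs B efficacy test in Section 9.4 without the randomization strata. It is valid and does not inflate type I error, but it is conservative: about 2-4% instead of 5% for assumed LDH hazard ratios of 2 to 4. Under an assumed constant hazard ratio of 0.70 the power loss is about 5-17 points over that range, about nil if LDH is weakly prognostic, and uncertain in size or even sign under non-proportional hazards.

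The response comparison, on its natural reading, drops patients who die or withdraw unscanned. It can favour the arm with more such losses. The size of this is unknown, and the 17% and 36% are illustrations only.

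A reader might infer that the trial's main conclusions are exposed. They are not. The primary endpoint, OS and the 3-year OS rate are named as ITT and use stratified tests, and PFS and response carry no stated alpha or power.

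**What to change.** In Section 9.4:

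1. Specify a stratified log-rank test (ECOG PS, LDH) for the A vs B PFS comparison. If a stratified Cox hazard ratio is reported, label it descriptive, given the position on proportional hazards in Section 9.3.
2. Name all randomized patients as the A vs B analysis set for PFS and response.
3. Count non-evaluable patients as non-responders in the A vs B response rate, and keep the 6.1.1 evaluable set as a sensitivity analysis.
4. Report the number of non-evaluable patients, with reasons, by arm.

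This takes a few phrases and needs no new data or patients. Reported response rates will be slightly lower than on the evaluable set. Under some non-proportional patterns the stratified PFS test may be slightly less powerful.
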